10.4.2 ANALYSIS OF THE PRIMARY EFFICACY ENDPOINT(S)

The primary outcome is volitional movement as measured by the brain motor control assessment (BMCA). The BMCA uses surface electromyography (sEMG) to track changes in muscle amplitudes relative to a population control in a normalized fashion. In this protocol, the lower extremity BMCA is used to track progress during the trial and is reported as a vector, which consists of the magnitude of the response vector (RV) and the similarity index (SI). The response vector is composed of the magnitudes of the sEMG where each dimension is an included muscle. The similarity index is the inner product of the normalized response vector in controls for a single maneuver with the normalized RV from the subject for that maneuver. The RV is reported in microvolts while the SI is reported as a value between 0 and 1, both continuous variables. As a pair, these are referred to as the voluntary response index (VRI).

The VRI for each maneuver will be averaged over all of the muscle groups at each appointment, resulting in a single sham vector and a single stimulation vector for each regularly scheduled appointment. By design, subjects undergoing the protocol should have response magnitudes and SI of 0 as baseline readings. By normalizing the VRI to (200, 1), it is possible to report a clinically significant change. For example, computing the normalized magnitude for a response magnitude of 50 uV and a SI of 0.2 would result in $\sqrt{(50/200)^2 + (0.2/1)^2} = 0.32$. Based on the limited data using this particular outcome, we feel a clinically significant change would be a distance of 0.2. This allows muscles groups to coordinate or improve in magnitude.

The primary outcome is whether subjects regain volitional movement during epidural stimulation. The hypothesis is then that the VRI should be higher during blinded treatment when compared to sham stimulation. While the time-course of change and measurements of plasticity are also interesting, the very small amount of pre-existing preliminary data available encourages efforts to focus on major changes in the primary outcome. For each subject,

we assume subjects will be able to attend at least 10 appointments, and, therefore, undergo 10 BMAC tests, resulting in 10 VRIs during treatment and sham.

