The repeated measures ANOVA will be used to compare sham and treatment where alpha is assumed to be 0.025 (two tailed) and power 0.95. The correlation between repeated measures is assumed to be 0.5. The ANOVA residuals will be assessed for normality and the groups will be assessed for homoscedasticity. If there are significant violations of these assumptions then Friedman's test will be used instead. The data will be displayed with means and 95% confidence intervals between treatment and sham for each subject and as a group over time.

Missing data will be analyzed to examine for randomness of omission. If the missing data is determined to be reasonably random, then predictive mean matching will be used for imputation. The distribution of the complete data set will be examined with and without the imputed data.

Data from subjects with incomplete data from dropout will be included in the final analysis unless the subject requested removal of their data. Incomplete data will be pooled per session.

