10.5 SAMPLE SIZE

Subjects will undergo blinded treatment and sham BMAC testing at each monthly appointment during the course of the trial. Assuming nonattendance to be approximately 25%, we expect subjects to complete at least 9 sessions. With a power of 0.95 and alpha of 0.025 for a two level ANOVA, we assume a correlation among repeat measure of 0.5. By assuming a baseline mean magnitude of 0.3 and a clinically significant change of 0.2 while assuming a within group standard deviation of 0.25 (resulting in an effect size of 0.4), we estimate that we will need at least 56 subjects to demonstrate significance for the primary outcome.

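### With about 25% of sessions expected to be missed, the primary analysis depends on an imputation rule that is too loosely specified to fix its error rate and has no branch for non-random missingness

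*Combined protocol and SAP*

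**What the plan says.** **Test.** Section 10.4.2: "The repeated measures ANOVA will be used to compare sham and treatment where alpha is assumed to be 0.025 (two tailed) and power 0.95". Friedman's test replaces it if the ANOVA assumptions fail. Each appointment contributes one sham value and one stimulation value.

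**Sessions.** Table 2 (Section 7.3.8) marks the Brain Motor Control Assessment (BMCA) at every month from 3 to 15, which is 13 post-implant sessions. Section 10.5 also describes monthly blinded testing.

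**Expected attendance.** Section 10.5: "Assuming nonattendance to be approximately 25%, we expect subjects to complete at least 9 sessions". Section 10.4.2 has a slightly different figure: "we assume subjects will be able to attend at least 10 appointments, and, therefore, undergo 10 BMAC tests".

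**Missing data.** Section 10.4.2: "If the missing data is determined to be reasonably random, then predictive mean matching will be used for imputation". The only check described is a look at the data distribution with and without the imputed values. Subjects who drop out stay in the final analysis unless they ask for their data to be removed. The paragraph ends: "Incomplete data will be pooled per session". Section 10.4.3 repeats this text for the standing and autonomic endpoints.

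**Analysis set.** Section 10.3 admits only subjects who complete at least 80% of the protocol.

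**The concern.** Repeated measures ANOVA laid out by condition and session, and Friedman's test in its standard form, both need every cell filled. At the attendance the plan expects, gaps are the normal state of the data, so the missing-data paragraph is a working part of the primary analysis.

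That paragraph leaves four things open:

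- It gives no criterion for the randomness judgement. Observed data cannot establish that missingness is random.
- It states no analysis for the case where the judgement goes the other way.
- It names predictive mean matching without saying which variables predict, how many data sets are imputed, or how results are combined. Both the sham and the stimulation value of a missed session have to be filled in, and these add no information about that subject's paired difference.
- The pooling sentence is undefined.

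Two analysts could follow the text faithfully and obtain materially different false-positive rates for the primary test. The choice between them would be made after data have been seen, and Sections 10.4.7.2 and 10.6.3 provide for unblinded interim looks.

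**Working it through.** **1. The plan's own sample size.** Inputs from Sections 10.4.2 and 10.5: "The correlation between repeated measures is assumed to be 0.5"; "By assuming a baseline mean magnitude of 0.3 and a clinically significant change of 0.2"; "assuming a within group standard deviation of 0.25 (resulting in an effect size of 0.4"); alpha 0.025, power 0.95, 9 sessions.

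- Effect size f = (0.2/0.25)/2 = 0.4.
- The repeated measures formula with a two-level between factor has noncentrality N·f²·m/(1+(m−1)ρ), with 1 and N−2 degrees of freedom.
- At N = 56, m = 9, ρ = 0.5: 56 × 0.16 × 9 / (1 + 8 × 0.5) = 80.64/5 = 16.13, power 0.9535.
- The smallest even N reaching 0.95 is 56, as stated. Ten sessions also gives 56.

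So sessions enter as repeated measures, and the expected loss of sessions is already allowed for.

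**2. How many subjects have every session.** With independent misses at 25%:

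| Scheduled sessions | Share complete | Of 56 |
|---|---|---|
| 13 | 0.75^13 = 2.4% | 1.3 |
| 12 | 3.2% | 1.8 |
| 10 | 5.6% | 3.2 |
| 9 | 7.5% | 4.2 |

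The documents do not say whether misses cluster within subjects. In a beta-binomial model with mean attendance 0.75 and 13 sessions, the complete share is 6%, 10%, 19% and 43% at assumed intraclass correlations of 0.05, 0.1, 0.2 and 0.5.

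**3. How much is imputed.** Cells: 56 × 13 × 2 = 1,456. A quarter of these is 364.

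**4. Effect on the test: reasoning.** If donors are chosen without regard to the subject, about 75% of each subject's mean difference is the subject's own and about 25% is drawn from other people. Where subjects differ in their response, their departures from the average shrink to roughly 0.75 of their true size. The overall mean varies from trial to trial as much as before. The computed standard error is then about 0.75 of the true one. With a two-sided critical value of 2.30 (55 degrees of freedom, alpha 0.025), the effective threshold is 2.30 × 0.75 = 1.73, a type I error of about 9%. At a ratio of 0.80 it is about 7%.

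**5. Effect on the test: simulation.** No mean effect, 56 subjects, 13 sessions, SD 0.25, correlation 0.5, 25% of sessions missing, single imputation, then a paired test on subject means. Assumed, because the documents give no figure: between-subject SD of the stimulation effect 0.1–0.2.

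| Handling of missed sessions | Type I error (planned 2.5%) |
|---|---|
| Matching on condition and month only | about 7–10%, SE 20–26% too small |
| Matching on the subject's overall mean, both conditions together | 7–9% |
| Matching on the subject's same-condition values | about 2–3% |
| Attended sessions only | about 2–3% |

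In a further run (assumed effect SD 0.15, matching on the subject's own mean difference), random missingness gave 3.1% with imputation and 2.9% with attended-session means. When attendance was made to depend on the subject's benefit, the figures were 3.9% and 2.1%. With a true effect of 0.2 and random missingness, all 500 simulated trials rejected under either method.

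**6. The 80% rule.** Section 10.3 conflicts with the inclusion of dropouts in Section 10.4.2. Read as sessions, 80% of 13 is 10.4, so at least 11. The chance of attending at least 11 of 13 is 33%, or 18.6 of 56 subjects. Among them the missed share is about 12%.

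**7. Secondary endpoints.** Table 2 gives standing 5 visits, so 0.75^5 = 24% complete. Autonomic assessments have at most 3, so 0.75^3 = 42%.

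**The case against.** **The plan never says every session is needed.** This stands. That requirement belongs to the condition-by-session layout and is not in the plan's words. The plan tests one two-level contrast and puts the time-course second, and an ANOVA on each subject's mean over attended sessions would lose nobody with at least one session. But the plan does not state that layout, and the undefined pooling sentence cannot stand in for it. If it were intended, imputation would be unnecessary, which supports the fix.

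**The inflated error rate depends on one way of running the imputation.** This also stands. A reader might infer that the primary test as planned has a 7–10% false-positive rate. The documents do not support that: they name the method without predictors or number of imputations, and a version using the subject's own same-condition values holds the rate near 2.5%. The defect is that the plan permits both.

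**The complete share depends on independence.** It does; hence the range. Section 7.3.3 names the BMCA only among the long-visit procedures, which would mean 5 sessions and 24% complete. Table 2 and Section 10.5 point to monthly testing.

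**A mixed model also assumes missing at random.** Correct. It removes the dependence on the imputation but cannot show that missingness is random, so a sensitivity analysis is needed as well. Imputation that conditions on subject and condition would perform about as well.

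**Conclusion.** The point holds as one of underspecification in the primary analysis and should be fixed. At the plan's expected attendance about a quarter of cells would be imputed, and most subjects would have at least one gap: nearly all if misses are independent, somewhat over half at the strongest clustering considered. Depending on choices the text leaves open, the type I error is about 2–3% or about 7–10%. These figures rest on the assumed between-subject effect SD of 0.1–0.2 and single imputation. The missing branch for non-random data and the conflict between Sections 10.3 and 10.4.2 need no assumption.

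Two stronger conclusions might be drawn and should not be. The result would not rest mainly on imputed data, since about three quarters of cells are observed. Nor is the sample size undermined: 56 reproduces at 9 attended sessions. The problem is smaller for the secondary endpoints, which have fewer visits and which Section 10.4.9 treats as preliminary.

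**What to change.** In Section 10.4.2:

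1. Make the primary analysis a linear mixed model on all attended sessions, with condition and month fixed and subject, subject-by-condition and subject-by-session random. A paired analysis of each subject's attended-session condition means would serve the same purpose. The two weight subjects slightly differently when attendance varies, so name one in advance. Use no imputation in either.
2. Delete the pooling sentence, or define it so that sham and stimulation stay paired within subject.
3. Add a sensitivity analysis that shifts the values of missed sessions over a stated range, to be run whatever the randomness check shows. If multiple imputation is kept as a further sensitivity analysis, condition it on subject-by-condition and state the number of imputations and the combining rule.
4. Reconcile the 80% analysis set in Section 10.3 with the inclusion of dropouts, and the 9 sessions in Section 10.5 with the 10 in Section 10.4.2.
5. Carry the same wording into Section 10.4.3.

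The cost is SAP wording and a small amount of extra analysis in standard software. It needs no new data or subjects, and N = 56 does not change.

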- Epidural hemorrhage, hematoma, spinal cord compression, or paralysis from placement of a lead in the epidural space
- Cerebrospinal fluid (CSF) leakage

- Paralysis, weakness, clumsiness, numbness, or pain below the level of the implant
- Seroma (mass or swelling) at the IPG site
- Allergic or rejection response to implant materials
- Implant migration or skin erosion around the implant

Potential Adverse Effects from Testing

- Skin abrasions
- Muscle damage from transfers
- Injury from Fall
- Hypotension
- Stroke

Participating in this trial is a significant commitment without guarantee of any benefit. Undergoing surgery, rehabilitation, and testing is a significant physical risk. Daily training and monthly appointments garner potential associated economic, social, and psychological risks including required travel for appointments and medical care, dissatisfaction with medical benefit, and prolonged postoperative recovery.

The risks associated with this study are warranted in humans because of the potential direct benefit of the study participants and the spinal cord injury community. There are no known alternative epidural spinal stimulation therapies to offer instead of surgical implantation.

Autonomic Testing

Many SCI subjects will likely sustain skin irritation from the recording electrodes. These conditions are considered to be minimal risks and are reversible.

There is some chance that subjects may sustain lowering or elevation of blood pressure, dizziness or skin abrasion from hand placements of the trainers. If these events occur, the experiment would cease immediately and the principal and co-principal investigators will be alerted if the condition persists. These conditions are considered to be minimal risks and are reversible.

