5.4.2 HANDLING OF PARTICIPANT WITHDRAWALS OR TERMINATION

Subjects may withdrawal from the study at any time. Subjects that choose to withdraw early from the study will be voluntarily surveyed for reasons for withdrawal. They will be asked for permission to continue to utilize the data collected up to the point of withdrawal for research purposes. Should they decline, all data past the note of withdrawal will be deleted from the record system. Subjects will not automatically have their stimulation device removed. Spinal cord stimulator devices will be removed electively, if the device malfunctions, or if the device poses a significant risk to the subject's health.

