10.3 ANALYSIS DATASETS

Subjects who complete at least 80% of the protocol will be included in the analysis data set.

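### Sections 5.4.2, 10.3 and 10.4.2 disagree on which of a withdrawing subject's data stay in the primary analysis, so subjects could be lost selectively

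*Combined protocol and SAP*

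**What the plan says.** Four places in the combined protocol and SAP govern what happens to a withdrawing subject's data.

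- **10.4.2 (primary endpoint):** "Data from subjects with incomplete data from dropout will be included in the final analysis unless the subject requested removal of their data". No date or visit limits what removal covers. The next sentence adds "Incomplete data will be pooled per session". The same two sentences appear in 10.4.3 under Standing Training and under Autonomic Function.
- **5.4.2 (withdrawals):** "They will be asked for permission to continue to utilize the data collected up to the point of withdrawal for research purposes". The sentence that follows is "Should they decline, all data past the note of withdrawal will be deleted from the record system". Withdrawing subjects are also surveyed, voluntarily, about why they left.
- **10.3 (analysis datasets):** "Subjects who complete at least 80% of the protocol will be included in the analysis data set". The section does not say how the 80% is counted.
- **10.4.2 (missing data):** missingness is examined for randomness, and "If the missing data is determined to be reasonably random, then predictive mean matching will be used for imputation". No action is given for the case where it is not random.

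No section plans a count of subjects removed at their own request, or a sensitivity analysis for them.

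**The concern.** The primary comparison is within subject: each attended session gives a stimulation and a sham value, and the estimate is the mean difference over subjects. Randomised, blinded testing within a session protects each subject's own contrast. It does not protect against selection of which subjects remain.

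Home training (7.1.1) uses active settings only, with no sham, over many months. Subjects enter with motor-complete paraplegia, so they can form their own view of whether stimulation moves their legs. Section 2.3.1 names among the risks of taking part "dissatisfaction with medical benefit, and prolonged postoperative recovery". A request to remove data could therefore be related to lack of response. If it is, and the request takes the whole subject out, the subjects lost are those with the smallest differences, and the estimate moves in favour of stimulation.

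Apart from bias, the rules as written do not define one primary data set. Two analysts could build different ones, each citing the protocol.

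**Working it through.** **1. The rules side by side.** Take a subject who withdraws after several paired sessions and refuses further use of data.

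| Section followed | Sessions recorded before withdrawal |
|---|---|
| 10.4.2, plain reading | Removed (no time limit) |
| 5.4.2, deletion sentence | Kept; only later data are deleted |
| 5.4.2, permission sentence | Use depends on the subject's permission, which implies that refusal ends it |
| 10.3 | Excluded if under 80% of the protocol, whatever the subject asked; otherwise not addressed |

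For a dropout who makes no request, 10.4.2 includes the data and 10.3 excludes them if completion is under 80%.

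The 10.3 rule could reach far. Table 2 marks the Brain Motor Control Assessment at months 3 to 15, which is 13 visits. If the 80% were counted on those visits (an assumption), a subject would need 11, since 0.80 × 13 = 10.4. Section 10.5 expects at least 9 sessions (9/13 = 69%) and 10.4.2 assumes at least 10 (10/13 = 77%).

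**2. The plan's own figure.** Inputs from 10.5: change 0.2, SD 0.25, correlation 0.5, 9 sessions. Section 10.4.2 gives "alpha is assumed to be 0.025 (two tailed) and power 0.95".

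- d = 0.2/0.25 = 0.8, so f = d/2 = 0.4, as stated.
- Noncentrality for a two-group repeated-measures ANOVA: λ = N·f²·m/(1 + (m − 1)ρ) = 56 × 0.16 × 9/(1 + 8 × 0.5) = 80.64/5 = 16.13, with 1 and N − 2 degrees of freedom.
- Power at N = 56 is 0.9535, and 56 is the smallest even N that reaches 0.95. The stated sample size is reproduced.

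This is a between-group formula although the comparison is within subject. It is used here only because it reproduces the plan's number.

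**3. Loss of whole subjects unrelated to outcome.** By the same formula, power is 0.942 with 53 subjects left and 0.927 with 50 left.

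**4. Loss related to outcome, effect present.** Suppose the mean difference over all 56 is 0.200 and m subjects with exactly zero difference are removed. The remaining mean is 0.200 × 56/(56 − m).

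- m = 3: 0.200 × 56/53 = 0.211 (+5.7%)
- m = 6: 0.200 × 56/50 = 0.224 (+12%)

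The values m = 3 to 6 (5% to 11% of 56) are assumptions. The 25% in 10.5 is nonattendance at sessions; it is not a dropout or removal rate.

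**5. Loss related to outcome, no true effect.** This simulation used a one-sample t-test on 56 subject-mean differences, an assumed SD of 0.25, 20,000 runs and nominal two-sided level 0.025. With nobody removed, the rejection rate was 0.024.

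| Removed | At random from the lower half | The lowest values (worst case) |
|---|---|---|
| 3 | 0.029 | 0.10 |
| 6 | 0.052 | 0.30 |

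**6. Whether the planned checks would catch it.** The randomness check in 10.4.2 needs outcome data. A subject whose data are removed entirely supplies none, so imputation cannot be guided by that subject's earlier sessions.

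**The case against.** The strongest reply is that this is a drafting ambiguity. Section 5.4.2 is the only place that describes a removal procedure, so removal in 10.4.2 may mean no more than what 5.4.2 deletes. Alternatively, the deletion sentence in 5.4.2 may be a slip for data before the note, in which case the two sections agree. Either reading is possible. They lead to opposite data sets, however, and nothing in the documents chooses between them.

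A reader might infer that the plan discards everything from a withdrawing subject, and that non-responders can leave once they know their result. The documents do not support that. The scope of removal in 10.4.2 is unstated, so total loss is the plain reading but not explicit. Clinic testing is blinded (10.6.1), the blind is broken only for interim and final analysis (10.6.3), and no section says that subjects are told their response index. What subjects do have is their own experience of open home stimulation, which is not the primary result.

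It is also fair to say that 2.3.1 lists dissatisfaction as a risk of participation, not as a reason for withdrawing data. Subjects may leave because of adverse events or travel. Outcome-related removal is plausible but not shown.

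The bias in step 4 is modest. With an assumed SD of 0.25 the standard error at 56 subjects is 0.25/√56 = 0.033, so shifts of 0.011 and 0.024 are each below one standard error. That stands as a limit on size, although step 5 shows that the error rate under no effect can rise well above nominal in the worst case.

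Finally, the plan does seek reasons for withdrawal and does examine missingness. Neither is tied to subjects whose data are removed.

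**Conclusion.** The inconsistency is established from the text. Section 5.4.2 does not agree with itself. Read literally, it does not agree with 10.4.2 and 10.4.3. Section 10.3 conflicts with the inclusion of dropouts in 10.4.2, and may exclude more subjects than the opt-out does.

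The bias is conditional. It requires that removal takes whole subjects and that requests are related to lack of response; the direction is then toward stimulation. Its size cannot be derived from the documents. Under the assumption of 3 to 6 zero-effect subjects removed of 56, the estimate rises from 0.200 to between 0.211 and 0.224. The point should be settled before the data are analysed, because the correction is cheap and the existing checks do not cover a fully removed subject. It does not show that the primary result will be biased.

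**What to change.** - **One rule.** Reconcile 5.4.2, 10.3, 10.4.2 and both places in 10.4.3. Stimulation and sham sessions recorded before the withdrawal note stay in the primary and secondary analyses, whether or not the subject reached 80% completion. The consent wording should match, subject to IRB approval. The consent pages are not in the available copy, so their present wording cannot be judged.
- **Reporting.** Where data must still be removed at a subject's request, report the number, the timing and any reasons given.
- **Sensitivity analysis.** Repeat the primary analysis with each removed subject's stimulation-minus-sham difference set to zero. This uses none of the removed data and so respects the request. With m = 3 in step 4 it returns 0.211 × 53/56 = 0.200. It is exact only if the removed subjects had no effect: it over-corrects if their differences were positive and under-corrects if they were negative.

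The cost is a sentence or so in each section, a consent change with IRB review, and one extra analysis. Subjects would have less say over data already collected than the permission request in 5.4.2 implies, and the sensitivity estimate may be slightly smaller than the main one.
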